#### *Propensity Score Matching*

Propensity score matching was first introduced in 1983. The technique summarises relevant baseline characteristics of each eligible HT patient into a single-index variable (the propensity score); HT patients in usual care will be matched to patients in the RAMP-HT group based on the value of the propensity score. The propensity score will be generated for each patient by logistic regression, modelling the RAMP-HT as dependent variable and baseline covariates of patients as independent variables. The propensity score mapping will be performed by using the “psmatch2” command with one-to-one matching without replacement and a callipers of 0.001 approach in the STATA.

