**b Introduction:**

Hypertension (HT) is an important risk factor for stroke, coronary heart disease (CHD), heart failure and renal diseases, and the leading risk factor of global disease burden. A multitude of interventions have proven efficacy in lowering blood pressure and reducing long term HT complications, including pharmacologic treatment, DASH diet (Dietary Approaches to Stop Hypertension), exercise, weight reduction, smoking cessation, alcohol moderation and self-monitoring of blood pressure. A few studies had examined the effects of coordinated multidisciplinary management programmes for HT patients to maximize the effectiveness of these interventions, but the long term benefit or cost-effectiveness of such programmes are uncertain.

In Hong Kong, over 200,000 patients with HT are being managed in public primary care clinics (i.e. General Out-patient Clinics (GOPCs) and Family Medicine Clinics (FMC)) under the Hospital Authority (HA); but more than 45% HT patients have still not achieved target blood pressure control (HA Internal communication). In order to improve the quality of care for patients with uncontrolled HT at GOPCs, the evidence-based , structured protocol-driven multidisciplinary Risk Assessment and Management Programme – Hypertension (RAMP-HT) was launched since October 2011 by the HA with the support from the Food and Health Bureau. Standardized cardiovascular risk factor assessment, hypertensive complication screening and assessment on patient adherence to treatment are carried out on enrolled patients (Appendix A). Patients are stratified into low,

medium or high risk groups according to the 10-year cardiovascular disease (CVD) risk calculated from their relevant risk factors by the Joint British Society 2005 Equation. A multidisciplinary team comprised of doctors, nurses, dieticians, physiotherapists and/or occupational therapists would then deliver individualized management targeted to the patient's risk factors according to standardized risk-stratified guidelines (Appendix B).

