##### **(ii) Subjects**

All patients who have enrolled into the RAMP-HT between 1 Oct 2011 and 31 March 2012, fulfilled the following inclusion criteria and without any exclusion criterion will be included in the RAMP-HT cohort. The same number of matched patients receiving usual care in GOPCs who have never enrolled into RAMP-HT on or before 31 March 2017, fulfilled the following inclusion criteria and without any exclusion criterion will be randomly selected from the HA clinical management system (CMS) to form the usual

care cohort.

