#### *Sample size calculation*

- a. For the long-term effectiveness evaluation, the difference in 5-year incidence of CVD between the RAMP-HT and usual care group is the primary outcome. From the result of our RAMP-HT QOC study, the observed 1-year incidence of CVD in the RAMP-HT and usual care group was 1.33% and 1.76% respectively. A conservative estimate of the 5-year incidence of CVD in RAMP-HT and usual care group would be 7% and 8%, respectively. A minimum sample size of 7,116 subjects from each group will be needed to detect a difference of 1% in incidence rates of CVD between RAMP-HT and usual care group with 90% power and at 5% level of significance.

We have identified from the HA CMS data set of the RAMP-HT QOC study 8,681 eligible RAMP-HT patients and 8,681 usual care patients who fulfilled the inclusion criteria and without any exclusion criterion matched by propensity score matching. These two matched cohorts will be the subjects of this long-term effectiveness and cost-effectiveness

study. The flow chart of subject selection is attached in Appendix C.

- b. For the costing analysis, 140 subjects from each of the RAMP-HT and usual care groups will be required to show that the direct medical costs of RAMP-HT patients (excluding RAMP cost) is not higher than that of usual care HT patients by independent one side t-test with 0.3 effect size and 80% power at 5% significance level.

307 RAMP-HT and 291 usual care patients had been recruited from May 2013 to March 2014 in GOPCs across Hong Kong for the longitudinal evaluation of patient reported outcomes (PRO) in the RAMP-HT QOC study. These patients will be follow-up from May 2015 to March 2016 as part of our RAMP-HT QOC study; telephone survey on private health service utilization will be conducted at the same time. Taking 25% attrition rate into account, 230 RAMP-HT and 218 usual care patients will complete the questionnaire. This sample will be adequate for the comparison of private medical cost between RAMP-HT and usual care group.

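### One-to-one matching leaves the 5-year CVD comparison at about 71% power, not the stated 90%; adding further in-calliper usual care records could raise it to roughly 79–88% without recruitment, if the eligible pool allows

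*Combined protocol and SAP*

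**What the plan says.** The Propensity Score Matching section specifies a logistic propensity score "with one-to-one matching without replacement and a callipers of 0.001 approach in the STATA". The Subjects section fixes the ratio in the same way: "The same number of matched patients receiving usual care in GOPCs" will be taken from the clinical management system (CMS), limited to people not enrolled in RAMP-HT by 31 March 2017.

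The Sample size calculation section, item a, makes the difference in 5-year CVD incidence the primary outcome. It assumes: "A conservative estimate of the 5-year incidence of CVD in RAMP-HT and usual care group would be 7% and 8%, respectively". It then states a minimum of 7,116 per group "with 90% power and at 5% level of significance", and reports that the matched cohorts already exist: "We have identified from the HA CMS data set of the RAMP-HT QOC study 8,681 eligible RAMP-HT patients" and an equal number of usual care patients.

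On the size of the source population, the Introduction says that "over 200,000 patients with HT are being managed in public primary care clinics" and that more than 45% of hypertensive patients are above target blood pressure. No section gives a reason for a 1:1 ratio.

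**The concern.** On paper, 8,681 per group exceeds a requirement of 7,116, so there appears to be no reason to look beyond one control per RAMP-HT patient. That comfort depends on the 7,116, which does not reproduce. With the correct requirement, 8,681 per group falls well short of 90% power for a 1-point difference.

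Usual care is the side that can most readily be enlarged. The study is retrospective, the usual care cohort is selected from routine records, and extra controls mean extra records rather than extra enrolment. At 1:1, usual care also contributes slightly more than half of the variance of the risk difference.

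The CVD result also feeds the economic model. The hazard ratios from the same cohorts adjust the Markov transition probabilities for the first five years, so their imprecision carries into the cost per QALY, which is another primary outcome.

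**Working it through.** **Inputs.** Risks of 7% and 8%, 90% power and 5% significance (Sample size calculation, item a). Two-tailed tests (Health Preference by HT Complication Status, closing paragraph). Chi-square test for CVD incidence (Long Term Effectiveness of RAMP-HT). 8,681 RAMP-HT patients. The plan states no allowance for censoring or loss on this endpoint, so none is applied.

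**1. The plan's own figure.** For equal groups, with mean risk 0.075:

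n = [1.960 × √(2 × 0.075 × 0.925) + 1.282 × √(0.07 × 0.93 + 0.08 × 0.92)]² / 0.01² = 14,577 per group.

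Variants at 90% power, two-sided: 14,574 unpooled, 14,777 with continuity correction, 14,564 arcsine, and about 14,533–14,580 from event-based formulas. One-sided, it is 11,881. None gives 7,116. Half of 14,577 is 7,289 and a one-sample formula gives 7,187, so a total read as a per-group figure, or a one-sample formula, may lie behind it; that is inference only. Power at 7,116 per group is 62.0%.

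**2. Power by control ratio.** With n₁ = 8,681, n₂ = k × 8,681 and p̄ = (0.07 + 0.08k)/(1 + k):

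- SE₀ = √[p̄(1 − p̄)(1/n₁ + 1/n₂)]
- SE₁ = √[0.07 × 0.93/n₁ + 0.08 × 0.92/n₂]
- power = Φ[(0.01 − 1.960 × SE₀)/SE₁]; 95% CI half-width = 1.960 × SE₁

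At k = 1, SE₀ = 0.003998 and SE₁ = 0.003997, so power = Φ(0.541) = 70.6%. The usual care share of SE₁² is 53%.

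| Effective ratio k | Effective controls | Power | Half-width (points) |
|---|---|---|---|
| 1 | 8,681 | 70.6% | 0.78 |
| 1.6 | 13,890 | 79.0% | 0.70 |
| 2 | 17,362 | 82.1% | 0.67 |
| 3 | 26,043 | 86.2% | 0.63 |
| 4 | 34,724 | 88.3% | 0.61 |

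Across continuity-corrected, unpooled and event-based versions, k = 1 gives 69.6–70.7% and k = 4 gives 87.8–89.8%.

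**3. What a variable ratio delivers.** If a RAMP-HT patient has m matched controls, each weighted 1/m, the weights sum to 8,681 and their squares sum to Σ(1/m). The effective number of controls is 8,681²/Σ(1/m), so the effective ratio is the harmonic mean of m. Illustrative mixes (assumed, not from the documents):

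- half with 1 and half with 4: 1/(0.5 + 0.125) = 1.6, power 79%
- equal quarters with 1, 2, 3 and 4: 1.92, power 82%
- 20% with 1 and 80% with 4: 1/(0.2 + 0.2) = 2.5, power 85%

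**4. The pool.** 200,000 × 0.45 = 90,000 uncontrolled patients before exclusions. A full 1:2 match needs 17,362, or 19% of that; a full 1:4 match needs 34,724, or 39%. The share that survives the eligibility criteria is not given.

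**The case against.** One-to-one matching is a legitimate design, and the actual error is the sample size statement. That is fair: the 7,116 needs correcting whatever is done about the ratio. But the correction exposes a shortfall, and adding controls is an inexpensive way to reduce it.

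Three stronger readings are tempting, and the documents do not support them.

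- **A reader might infer that 1:1 matching throws away most eligible usual care records.** That needs more than 17,362 eligible controls. The 90,000 precedes the exclusions for age, prior complications, diabetes up to March 2017, specialist-only care and any RAMP-HT enrolment over the following five years. The last of these draws on exactly this population. The selection flow is in Appendix C, which is not in the text available for review.
- **A reader might infer that matching up to four controls would give 88% power.** That figure needs four in-calliper controls for every RAMP-HT patient, without replacement, at 0.001. With unequal set sizes and 1/m weights the gain is smaller, as step 3 shows.
- **A reader might infer that the enrolment window fixes the RAMP-HT side at 8,681.** The plan describes both groups of 8,681 as matched, so this may be a post-match count. If some RAMP-HT patients found no match even at 1:1, overlap may already be thin and extra matches scarcer.

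The benefit also depends on the effect. The plan calls 7% against 8% conservative. Applying its observed 1-year ratio (1.33/1.76 = 0.756) to 8% gives about 6.05%, and power at 1:1 is then above 99%. The shortfall concerns the scenario on which the plan chose to base its size, not every plausible effect.

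**Conclusion.** The point holds as a worthwhile improvement tied to a definite error. The definite part is that 8,681 per group gives about 71% power for 7% against 8%, so a true 1-point benefit would be missed about 29% of the time, where the plan's 90% implies 10%.

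The conditional part is the gain. If further in-calliper controls exist, power rises to about 79–88% for effective ratios of 1.6 to 4. Even a full 1:4 match stays just under 90% by the pooled formula, which would need 9,178 RAMP-HT patients. Provided each first match is kept, extra weighted controls do not reduce precision.

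The calculation assumes the planning risks, two-sided testing, no loss to follow-up, and a usual care pool probably larger than 8,681. The last is an assumption that the sponsor can check against its own pre-matching count.

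**What to change.** 1. Correct the sample size statement: about 14,577 per group are needed at 1:1 for 90% power, and the 8,681 available give about 71%.
2. Report the number of eligible usual care patients, and of eligible RAMP-HT patients, before matching.
3. Keep each existing first match, then add up to three further usual care patients per RAMP-HT patient, using the same score and 0.001 calliper, without replacement. Weight each control by one over the number matched to that patient. Weighting all eligible usual care patients to the RAMP-HT cohort is an alternative; its precision was not calculated here.
4. Check covariate balance in the weighted sample. Use the weights in the Cox model and the 5-year risks, with matched-set or robust standard errors.
5. Restate power for the effective ratio actually achieved. The 1:1 set can be kept for the costing work.

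**Cost.** No recruitment. Up to 3 × 8,681 = 26,043 further patients would need full five-year outcome data, whereas the existing cohorts already have three years from the earlier quality-of-care study. The HK$100,000 extraction line may therefore not be enough. Later matches will be slightly less close, within the unchanged calliper, and the analysis becomes a weighted one.

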#### *Sample size calculation*

- a. For the long-term effectiveness evaluation, the difference in 5-year incidence of CVD between the RAMP-HT and usual care group is the primary outcome. From the result of our RAMP-HT QOC study, the observed 1-year incidence of CVD in the RAMP-HT and usual care group was 1.33% and 1.76% respectively. A conservative estimate of the 5-year incidence of CVD in RAMP-HT and usual care group would be 7% and 8%, respectively. A minimum sample size of 7,116 subjects from each group will be needed to detect a difference of 1% in incidence rates of CVD between RAMP-HT and usual care group with 90% power and at 5% level of significance.

We have identified from the HA CMS data set of the RAMP-HT QOC study 8,681 eligible RAMP-HT patients and 8,681 usual care patients who fulfilled the inclusion criteria and without any exclusion criterion matched by propensity score matching. These two matched cohorts will be the subjects of this long-term effectiveness and cost-effectiveness

study. The flow chart of subject selection is attached in Appendix C.

- b. For the costing analysis, 140 subjects from each of the RAMP-HT and usual care groups will be required to show that the direct medical costs of RAMP-HT patients (excluding RAMP cost) is not higher than that of usual care HT patients by independent one side t-test with 0.3 effect size and 80% power at 5% significance level.

307 RAMP-HT and 291 usual care patients had been recruited from May 2013 to March 2014 in GOPCs across Hong Kong for the longitudinal evaluation of patient reported outcomes (PRO) in the RAMP-HT QOC study. These patients will be follow-up from May 2015 to March 2016 as part of our RAMP-HT QOC study; telephone survey on private health service utilization will be conducted at the same time. Taking 25% attrition rate into account, 230 RAMP-HT and 218 usual care patients will complete the questionnaire. This sample will be adequate for the comparison of private medical cost between RAMP-HT and usual care group.

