**Long Term Effectiveness of RAMP-HT**

Descriptive statistics will be performed on the clinical parameters (e.g. blood pressure (BP), lipid profile, BMI) and incidence of CHD, heart failure, stroke, ESRD, HT-related mortality and all-cause mortalities of the RAMP-HT and usual care cohorts. Differences in each outcome between groups will be tested using independent t-tests for continuous variables such as mean BP, or chi-square tests for categorical variables such as proportion of patients with BP control or CVD incidence. The number needed to treat to reduce one CVD, each specific HT complication and death by RAMP-HT will be calculated from the unadjusted 5-year rates between RAMP-HT and usual care HT cohorts.

Multivariable Cox proportional hazards regression will be performed to estimate the adjusted effect of RAMP-HT on the dependent variable of each first HT complication event, adjusting for all baseline covariates of patients. Cox model has been widely used to evaluate the effectiveness of primary care intervention in previous study. For each model, survival curves will be estimated by Kaplan-Meier method and the differences between RAMP-HT and usual care groups will be compared using the

log-rank test. The effectiveness of RAMP-HT will be measured by Hazard ratio with 95% confidence intervals in the regression models. Predictive accuracy of Cox models will be assessed and compared using Harrell's discrimination C-index, ranging from zero to one. A value of 0.5 indicates no predictive discrimination, and values of 0 or 1.0 indicate perfect separation of patients. Goodness-of-fit for Cox regression model will be assessed using Akaike information criterion and Bayesian information criterion.

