### **Health Preference by HT Complication Status**

The SF-6D preference will be calculated by the HK population specific

algorithm^15 by HT complication status. Independent t-test will be used to compare the SF-6D values of HT patients with each complication to those without any complication, and between RAMP-HT and usual care HT patients.

All above statistical analyses will be performed using STATA Version 13.0 (StataCorp LP. College Station, Texas, U.S.). All significance tests will be two-tailed and those with a p-value less than 0.05 will be considered statistically significant.

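### The planned 7,116 per group gives about 62% power, not 90%, for 7% vs 8% CVD; the 8,681 per group available give about 71%

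*Combined protocol and SAP*

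**What the plan says.** The sample size section (section d(ii), Sample size calculation, item a) states that "the difference in 5-year incidence of CVD between the RAMP-HT and usual care group is the primary outcome". It sets the planning rates: "A conservative estimate of the 5-year incidence of CVD in RAMP-HT and usual care group would be 7% and 8%, respectively". From these it concludes: "A minimum sample size of 7,116 subjects from each group will be needed to detect a difference of 1% in incidence rates of CVD", "with 90% power and at 5% level of significance". The next paragraph reports that "8,681 eligible RAMP-HT patients and 8,681 usual care patients" have been identified and will form the study cohorts.

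The other inputs are elsewhere in the plan:

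- **Test:** the Long Term Effectiveness section uses "chi-square tests for categorical variables such as proportion of patients with BP control or CVD incidence", alongside log-rank tests and Cox regression.
- **Sidedness:** the end of the Health Preference by HT Complication Status section says "All significance tests will be two-tailed and those with a p-value less than 0.05 will be considered statistically significant".
- **Allocation:** the propensity score section specifies "one-to-one matching without replacement".

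Item a mentions no one-sided test, paired test, within-pair correlation or dropout allowance for this comparison. The sentence cites reference 18, which the reference list gives as a Hospital Authority annual report, so the formula used cannot be traced.

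**The concern.** A 1-point difference between rates near 7.5% is small, and 7,116 per group looks too few to detect it with 90% power. The figure matters because it is the plan's only statement on whether the first listed primary outcome is adequately powered. A reader who sees 8,681 available against a minimum of 7,116 will conclude that the study has more than 90% power with a margin.

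If the figure is wrong, a non-significant CVD result would be read against a false benchmark and could pass for evidence of no long-term benefit. The hazard ratio from the same analysis also adjusts the transition probabilities in the Markov model, and the plan says the results can inform policy on such programmes.

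**Working it through.** **Inputs.** p1 = 0.07 and p2 = 0.08 (item a); two-sided 5% level (item a and the two-tailed rule); 90% power (item a); two independent groups, 1:1 (chi-square test, one-to-one matching). Mean rate = 0.075.

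**1. Attempt to reproduce 7,116.** The pooled-variance formula for two proportions is

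n per group = [z(0.975) × √(2 × 0.075 × 0.925) + z(0.90) × √(0.07 × 0.93 + 0.08 × 0.92)]² / 0.01²

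= [1.9600 × 0.37249 + 1.2816 × 0.37242]² / 0.0001

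= [0.73007 + 0.47728]² / 0.0001 = **14,577**.

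The stated figure is not reproduced: 7,116 / 14,577 = 0.49.

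**2. Other versions of the calculation (7% vs 8%, per group).**

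| Version | Required n |
|---|---|
| Two-sided, 90%, unpooled variance | 14,574 |
| Two-sided, 90%, arcsine | 14,564 |
| Two-sided, 90%, continuity-corrected | 14,777 |
| Two-sided, 90%, log-rank (Schoenfeld) | about 14,533 |
| One-sided, 90% | 11,881 |
| Two-sided, 80% | 10,890 |
| One-sided, 80% | 8,578 |

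All exceed 7,116.

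**3. Power at the stated and available sizes.** Power = Φ{[0.01 × √n − 0.73007] / 0.37242}.

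- n = 7,116: (0.84356 − 0.73007) / 0.37242 = 0.305, so power is **62.0%** (60.8% with continuity correction).
- n = 8,681: (0.93172 − 0.73007) / 0.37242 = 0.541, so power is **70.6%** (69.6% with continuity correction).

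One-sided at 5%, these become 73.2% and 80.4%, still short of 90%.

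**4. Time-to-event check.** The planned rates imply a hazard ratio of ln 0.93 / ln 0.92 = 0.870. Schoenfeld's formula needs 4 × (1.9600 + 1.2816)² / (ln 0.870)² ≈ 2,180 events. The cohort is expected to give 8,681 × (0.07 + 0.08) ≈ 1,302. Log-rank power is 70.7%, so the log-rank analysis does not change the answer.

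**5. What 8,681 per group can detect.** With usual care at 8.31% against 7.0%, power is 90.1%. With RAMP-HT at 6.71% against 8.0%, it is 90.3%. The difference detectable with 90% power is therefore about 1.3 points.

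**6. Where 7,116 might come from.** This is conjecture. It is close to half the correct number, as if the factor of two for comparing two groups had been lost: a one-sample formula gives 7,187 to 7,374. The two-group formula for 3% vs 4% gives 7,096, but those rates are not in the plan. None of these gives exactly 7,116.

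**The case against.** Three arguments favour the plan.

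**The planned effect is deliberately cautious.** Item a also gives observed 1-year rates of 1.33% and 1.76%. Compounding them over five years at a constant rate gives 1 − 0.9867⁵ = 6.5% and 1 − 0.9824⁵ = 8.5%, for which 8,681 per group has about 99.9% power. Simple multiplication by five gives 6.65% vs 8.80%, for which 3,239 per group suffice for 90% power. This stands as a limit on the consequence: the study may be well powered in fact. It does not make the statement correct, because the plan claims 90% power for 7% vs 8%. That the 1-year gap will last five years is also an assumption.

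**The cohorts are matched, so a paired calculation might need fewer subjects.** A McNemar calculation reaches about 7,120 pairs only if about 6.8% of pairs are discordant. Independence gives 0.07 × 0.92 + 0.08 × 0.93 = 13.9%, so this needs a within-pair correlation of about 0.5. The plan states no such correlation and no paired test. This does not rescue the figure.

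**The cohort is fixed and retrospective, and hazard ratios will be reported with 95% confidence intervals.** Correcting the number changes no patient, endpoint or analysis, and the intervals will show the precision achieved. Both points are fair. Nor does the plan say that it would read a null result as no benefit. But the power statement remains wrong, and the plan's analysis of this same cohort cannot cure the shortfall by adding patients.

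**Conclusion.** The concern holds. For the plan's own 7% vs 8%, two-sided 5% and unpaired comparison, 90% power needs about 14,577 per group, roughly twice the stated minimum and 1.68 times the 8,681 available. Power is about 62% at 7,116 and about 71% at 8,681, so a true 1-point difference would be missed about 29% of the time.

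These figures take the planned rates at face value, treat the groups as independent and allow for no loss to follow-up. The two-tailed rule is a general statement in the plan, since item a does not give sidedness, but a one-sided reading also falls short. The origin of 7,116 is unknown and the conclusion does not depend on it. How well the study is powered in truth depends on the real 5-year difference; the error lies in the stated number and the power attached to it.

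**What to change.** Rewrite item a of the sample size section to state that:

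- detecting 7% vs 8% with 90% power at a two-sided 5% level needs about 14,577 per group;
- the fixed cohort of 8,681 per group gives about 71% power for that difference;
- the same cohort gives 90% power for a difference of about 1.3 points (for example 7.0% vs 8.31%).

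Name the formula and test, state the sidedness in the paragraph itself, and correct the reference so that the calculation can be traced. The scenario from the observed 1-year rates (about 6.5% vs 8.5%, over 99% power) can be shown beside this as a sensitivity case, with its constant-rate assumption stated. It should not simply replace 7% vs 8%, because that would be choosing the effect to fit the available sample.

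The cost is one paragraph. No patients, data or analyses change; the stated power becomes less favourable.

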#### Exclusion criteria

1. Patients who had a diagnosis of any HT complications defined by relevant ICPC-2 and/or ICD-9-CM diagnosis codes (defined in the "Methods" section) on or before baseline\*
2. Patients diagnosed to have Diabetes Mellitus (DM) on or before 31 March 2017, defined by ICPC-2 codes of T89 or T90
3. Patients exclusively managed by Specialist Out-Patient Clinic (SOPC) on or before baseline\*

To reduce selection bias, the RAMP-HT and usual care subjects will be matched in baseline covariates using the propensity score matching method:

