**HA CMS Data Extraction of Incidence of HT Complications and All-cause Mortality**

Our RAMP-HT QOC study will have collected anonymous 3-year follow up HA CMS data of the cohorts available by November 2015. This study plans to extend the follow up period for an additional 2 years to measure the 5-year incidence of CVD, ESRD and mortality outcomes of these HT patient cohorts from 1 Oct 2011 to 31 March 2017. The data extraction will be carried out by the HA statistics team. Each patient in the cohorts (RAMP-HT and usual care groups) will be observed from baseline to the first occurrence of any of the outcome events until 31 March 2017, with CMS documented diagnoses defined by the relevant ICPC-2 and ICD-9-CM codes below:

1. Cardiovascular disease (CVD) is defined as the presence of any of coronary heart disease (CHD), heart failure or stroke. CHD includes all ischaemic heart disease, myocardial infarction (MI), coronary death or sudden death as indicated by the ICPC-2 K74 to K76 or ICD-9-CM 410.x, 411.x to 414.x, 798.x codes. Heart failure is defined as the ICPC-2 K77 or ICD-9-CM 428.x codes. Stroke (fatal and non-fatal stroke) is defined by the ICPC-2 K89 to K91 or ICD-9-CM 430.x to 438.x codes.
2. End Stage Renal Disease (ESRD) is defined by any of ICD-9-CM 250.3x, 585.x, 586.x, or an estimated Glomerular Filtration Rate (eGFR)  $<15\text{mL/min}/1.73\text{m}^2$ , according to the definition of the National Kidney Foundation.
3. Mortality is defined by a documented death in the Hong Kong Death Registry.

The definitions of each HT complication are determined by the clinician co-investigators and endorsed by clinicians of the HA.

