#### e Timeline

Project timeline (0-24 month)	Work Phase	Milestones
----------------------------------	------------	------------

April – July, 2016 (0-4 month)	Study planning	
 
a) Recruitment, training of RA and literature review
 
b) Data schema and operational definition confirmation with the HA Statistics Team
 
c) Costing data collection questionnaires development and field testing
 
d) Extraction of 3-year outcome and public medical cost data from HA CMS data for interim analysis
 

August – November, 2016 (4-8 month)	Cost Data Collection	
 
a) Costing data collection
 
b) Feedback on results of cost of RAMP-HT to HA RAMP-HT programme team to assure validity
 

December, 2016 – March, 2017 (9-12 month)	Preliminary Model development based on 3-year data	
 
a) Analysis of annual direct public and private medical costs of RAMP-HT & usual care subjects
 
b) Preliminary analysis of ICER of RAMP-HT Vs. usual care
 

April– November, 2017 (13-20 month)	Final Data analysis	
 
a) Extraction of 5-year outcome and public medical cost data from HA CMS
 
b) To evaluate the 5-year long-term effectiveness of RAMP-HT
 
c) Final Markov model on cost-effectiveness of RAMP-HT based on 5-year outcome and cost data.
 

December, 2017 – March, 2018 (21-24 month)	Preparation of final report and manuscripts	
 
a) Two manuscripts for submission to peer-reviewed international journals
 
b) Final report ready for submission
 

		before September, 2018.
--	--	-------------------------

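### The 8,681 matched patients per group cannot be confirmed as the analysed size, because two eligibility criteria run to 31 March 2017 and could not be fully applied when they were counted

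*Combined protocol and SAP*

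**What the plan says.** Section d(ii), Sample size calculation, item a, reports in the past tense that the team has identified "8,681 eligible RAMP-HT patients and 8,681 usual care patients who fulfilled the inclusion criteria and without any exclusion criterion matched by propensity score matching". It continues: "These two matched cohorts will be the subjects of this long-term effectiveness and cost-effectiveness" study. The same item sets a minimum of 7,116 subjects in each group.

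Two eligibility rules reach beyond baseline, to the last day of follow-up:
- Section d(ii) Subjects admits to usual care only patients "who have never enrolled into RAMP-HT on or before 31 March 2017". This rule applies to one group.
- Exclusion criterion 2 removes "Patients diagnosed to have Diabetes Mellitus (DM) on or before 31 March 2017". This rule applies to both groups.

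On timing, section d(iv), HA CMS Data Extraction, says: "Our RAMP-HT QOC study will have collected anonymous 3-year follow up HA CMS data of the cohorts available by November 2015". It then says: "This study plans to extend the follow up period for an additional 2 years". The Timeline (section e) starts the project in April 2016 and places "Extraction of 5-year outcome and public medical cost data from HA CMS" in April to November 2017.

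Matching is "one-to-one matching without replacement and a callipers of 0.001 approach in the STATA". Section d(v), Long Term Effectiveness, compares the cohorts with independent t-tests, chi-square tests and log-rank tests, takes the NNT from unadjusted 5-year rates, and fits Cox models adjusted for all baseline covariates.

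**The concern.** A cohort counted before November 2015 cannot have been screened for events up to 31 March 2017. Either the 8,681 per group were screened to some earlier, unstated date, or the two criteria were not applied as written. In both cases the count does not establish what the sample size section says it does.

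When the 5-year extract arrives, following the plan as written means removing patients who were already matched. The diabetes rule can take either member of a pair; the enrolment rule takes only the usual care member. The visible text gives no rule for such removals, for rechecking balance, or for restating the sample size. The analysts would have to choose, with outcome data in hand, between keeping patients who breach the stated criteria and analysing unequal groups that are no longer matched. That choice affects the comparison of 5-year CVD incidence, a primary outcome, and the NNT, a secondary one. Neither the chi-square test nor the NNT has any covariate adjustment to fall back on.

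**Working it through.** **1. Dates.** The latest date to which the two criteria apply is 31 March 2017. The plan speaks of the 3-year data as still to be collected by November 2015 (section f gives 30 November 2015). The cohorts had already been identified by then, so the count precedes the cut-off by at least 16 months (end of November 2015 to end of March 2017). The 5-year extraction begins in April 2017. Status to the cut-off was unknown when the 8,681 were counted.

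**2. The plan's own minimum.** Inputs from the sample size section: 7% versus 8%, 90% power, 5% level; two-sided, since section d(v) says tests are two-tailed. Per group:

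n = [1.960·√(2 × 0.075 × 0.925) + 1.282·√(0.07 × 0.93 + 0.08 × 0.92)]² / 0.01² ≈ [0.7301 + 0.4773]² / 0.0001 ≈ 14,577.

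The stated 7,116 is not reproduced. Two-sided power is 62.0% at 7,116 per group and 70.6% at 8,681. That is a separate matter. It means 7,116 can be used here only as the plan's own yardstick, and the apparent spare of 8,681 − 7,116 = 1,565 patients per group is not real spare capacity at 90% power.

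**3. Effect of applying the criteria after matching.** The documents give neither a diabetes incidence nor a late-enrolment rate, so both are assumptions. Let d be the share of each group removed for diabetes not already screened out, and x the share of the remaining usual care patients removed for later RAMP-HT enrolment. The stated minimum is per group and the planned tests are unpaired, so the count is per arm:

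- RAMP-HT: 8,681 × (1 − d)
- Usual care: 8,681 × (1 − d) × (1 − x)

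| d (assumed) | x (assumed) | RAMP-HT | Usual care | Two-sided power, 7% vs 8% |
|---|---|---|---|---|
| 0% | 0% | 8,681 | 8,681 | 70.6% |
| 1% | 0% | 8,594 | 8,594 | 70.2% |
| 2% | 5% | 8,507 | 8,082 | 68.6% |
| 5% | 10% | 8,247 | 7,422 | 66.1% |
| 8% | 20% | 7,987 | 6,389 | 62.1% |

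**4. Break-even against 7,116.** With d = 5%, 8,681 × 0.95 = 8,247 usual care patients remain before the enrolment rule, and they fall below 7,116 when x > 1 − 7,116/8,247 ≈ 13.7%. With d = 0 the threshold is 1 − 7,116/8,681 = 18.0%. RAMP-HT stays above 7,116 throughout the table.

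**5. Balance.** Any x above zero removes patients from one arm only, on the basis of something that happened after baseline. The covariate distribution of those who remain need not match that of the RAMP-HT arm. The size of this effect cannot be calculated from the documents.

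**The case against.** The strongest reply is that the practical effect may be small. The count may already exclude everyone known to fail up to the date it was made, leaving only later events to remove. The tests are unpaired, so losing one member of a pair does not invalidate them or require its partner to be discarded. The Cox models adjust for every baseline covariate. Sections d(ii) Subjects and Propensity Score Matching also use the future tense, which could mean that selection and matching will be run again, and the flow chart in Appendix C is not available to settle which cut-off was used.

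Most of this stands as a limit on size. A reader might count only intact pairs, 8,681 × (1 − d)² × (1 − x), and find that 5% diabetes with 10% enrolment leaves 7,051, below the minimum. The documents do not support that reading: nothing in the plan discards the partner, 7,116 is a number per group, and on the same assumptions both arms (8,247 and 7,422) stay above it.

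The reply does not remove the inconsistency. If matching is to be repeated, the statement that the existing cohorts will be the subjects is wrong, and so may be the 8,681. If it is not, the criteria will be applied to groups already matched. No flow chart of that date could hold status to March 2017.

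**Conclusion.** The inconsistency is established from the plan's own dates: the 8,681 per group cannot be confirmed as the analysed size under the stated criteria. For fixed cohorts, applying those criteria can only reduce it, and the enrolment rule reduces usual care alone. The likely consequences are unequal arms and weaker balance for the unadjusted chi-square tests and the NNT, with less effect on the adjusted Cox models.

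The size is not known. Under assumed rates of 5% and 10%, the arms are 8,247 and 7,422 and power moves from 70.6% to 66.1%. Usual care drops below the plan's minimum only above about 13.7% later enrolment, given 5% diabetes. These figures assume equal diabetes rates in both groups and no re-matching.

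A reader might go further and say that 8,681 is certainly wrong, that the stated minimum will be missed, or that matched balance will be lost. The documents support none of these as a certainty, because they give no loss rates. Nor does the power shortfall come mainly from this issue: most of it is present at 8,681 per group, before anyone is removed.

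**What to change.** Preferred: define both criteria at the baseline date (RAMP-HT enrolment date, or 31 March 2012 for usual care), so that nobody is removed from the matched cohorts for later events. Treat later diabetes or RAMP-HT enrolment as events during follow-up: for example, keep patients in the group they belonged to at baseline in the main analysis, and censor at the event in a sensitivity analysis. State which cut-off produced the 8,681 and confirm the count under the baseline rules. This comes first because it also stops eligibility from depending on what happened after baseline.

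Alternative, if the 2017 cut-offs are kept: apply them to the full eligible source pools, re-estimate the propensity score and re-match once before outcomes are analysed, recheck balance, and restate the number per group and its power. This repairs the count and the matching but retains selection on post-baseline events.

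Cost: for the preferred route, changes to two criteria, a short sensitivity analysis and a recount. The number may change, particularly if the existing count already dropped patients for events after baseline. The alternative also needs data to March 2017 for the source pools, whereas the plan extends follow-up only for the existing cohorts.
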